3.3 Other study parameters

We will gather the data about the following data of our cases; age and sex of the child, obstetric medical data and neonatal characteristics and morbidity of the study population. Parents will be asked to complete a questionnaire to assess the highest level of education of the parents. We use this data to describe our study population and correct for potential confounding of these factors on neurodevelopmental outcome as described in chapter 11. Study parameters are summarized in Table 1, a list of definitions can be found in Table 3.

Possible confounding factors for allergies are the family history for asthma, allergies or eczema. For evaluation of the infections it is important to assess smoking at home and day-care visit as possible confounding factors.

Table 1: Study parameters

Study parameters		
Obstetric data	Maternal characteristics	Age mother at delivery Obstetric history Medication usage during pregnancy
	Pregnancy characteristics	Gravidity/Parity Pregnancy induced hypertension Pre-eclampsia Signs of bleeding in the fetus at ultrasound
	FNAIT related therapy	IVIg treatment Intra-uterine transfusions Treatment with corticosteroids
	Labour characteristics	Mode parturition Gestational age at delivery
	Placental features	Placenta weight
Neonatal data	Birth data	Gestational age at birth Birthweight Apgar score
	Severe neonatal morbidity	Respiratory distress syndrome Perinatal asphyxia Proven early onset neonatal sepsis Retinopathy of prematurity Necrotizing enterocolitis
	Neonatal neurologic sequelae	Intracranial haemorrhage Cystic periventricular leukomalacia Ventricular dilatation Porencephalic or parenchymal cysts Convulsions Any cerebral lesions associated with adverse neurologic outcome
	Signs of bleeding	Skin manifestations Intracerebral bleeding Organ bleeding Increased bleeding tendency, reported by the caregiver
	Therapy	Platelet transfusions IVIg treatment

Table 1: Study parameters

[figure not shown]
Study parameters		
Laboratory data	HPA	HPA incompatibility HPA genotyping Anti-HPA-titre Platelet count Directly after birth Nadir Other Presence of HLA class I antibodies

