5.2 Inclusion criteria

In order to be eligible to participate in this study, a subject must meet all of the following criteria:

- Children diagnosed with FNAIT during pregnancy or postnatal, at moment of inclusion 2 to 16 years of age.
- Children living in the Netherlands.
- Parents or guardian aged ≥ 18 years old, with parental authority.
- Written informed consent form both parents with, form being approved by Ethic Committee.

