9.1.3 Other study parameters

An inventory will be made of the following confounders gender, obstetrical and neonatological complications and education level of the parents according to the International Classification of Education. [25] We will assess the family history of allergies asthma and eczema to obtain information about possible confounding factors in our study groups. Also smoking and day-care visit will be questioned.

Table 2: Overview assessments

Study assessments			
Age group	Name assessment tool	Abbreviation	Outcome
Cognitive development			
2-3 years	Bayley scales of infant and toddler development third edition.	Bayley III	IQ score
4-6 years	Wechsler Preschool and Primary Scale of Intelligence third edition.	WPPSI III	IQ score
7-16 years	Wechsler Intelligence Scale for Children fifth edition	WISC V	IQ score
Motor development			
2-3 years	Bayley scales of infant and toddler development third edition	Bayley III	Motor test score
2-18 years	Neurologic Examination According to Touwen.	Touwen	Gross Motor Function Classification System
Quality of life			
5-7 years	Pediatric Quality of Life Inventory	PedsQoL	Health related quality of life score
8-12 years	Pediatric Quality of Life Inventory	PedsQoL	Health related quality of life score
Behaviour			
1.5-5 years	Child Behavior Checklist	CBCL	Behaviour test score
6-18 years	Child Behavior Checklist	CBCL	Behaviour test score
Course of infections			
2-18 years	Questionnaire based on 'Richtlijn diagnostiek naar onderliggende aandoeningen bij kinderen met recidiverende luchtweginfecties'		Indication for diagnostic evaluation by immunologist; Yes/No.

Table 2: Overview assessments

Study assessments			
Age group	Name assessment tool	Abbreviation	Outcome
Atopic constitution			
2-18 years	Questionnaire composed in collaboration with allergist ([name]).	(Parent reported)	Allergy
Severity of asthma and hay fever			
6-18 years	Control of allergic rhinitis and asthma test.	CARATkids	CARATkids score

Table 3: Definitions of outcome

Definitions of outcome		(1/3)
Outcome parameter	Definition	
Obstetric medical data		
Pregnancy induced hypertension	De novo hypertension (blood pressure above 140/90 mmHg) after gestational week 20.[26]	

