Intracerebral bleeding	Any bleeding in the cerebral cavity.	
Organ bleeding	Bleeding in any organ located in the thorax or abdomen.	
Postpone bleeding	Postpone bleeding that was noted as sign of bleeding by the caretaker.	
Skin manifestations	Petechiae, purpura or hematoma diagnosed by the caretaker at neonatal period (gynecologist, pediatrician or midwife).	
Neonatal IVIG treatment	Any administration of IVIG after birth.	
Platelet transfusion	Any platelet transfusion.	
Neurodevelopmental impairment		
Cerebral Palsy	Spastic bilateral, spastic unilateral or mixed Classification by European CP Network [19].	
Impaired cognitive or motor development	Score < 70 (2 SD below the mean) as assessed by Bayley Scales of Infant and Toddler Development version 3 (BSID III) [16]	
Bilateral blindness	Blind or partially sighted.	
Bilateral deafness	Needing hearing aids.	

Definitions of outcome		(3/3)
Outcome parameter	Definition	
Secondary outcomes		
Abnormal course or incidence of infections	Need to refer to an immunologist or the need to perform diagnostics based on history taking according to the Dutch guidelines. [23]	
Prevalence of allergies	Parent reported allergy.	
Patient reported anaphylaxis	Serious allergic reaction, requiring urgent medical treatment with epinephrine.	
Poor control of allergic rhinitis	CARAT score of upper airways < 8.[22, 33]	
Poor control of asthma	CARAT score of lower airways < 16.[22, 33]	
Prevalence of eczema	Parent reported eczema.	
Demographic characteristics		
Ethnic origin of the parents	Ethnic origin of mother and father.	
Educational level of the parents	Highest level of graduation of the parents.	
Smoking	Any person living in the household of the child smoking one or more cigarettes a day.	
Day-care visit	When child is in day care at least one day a week.	
Family history (first degree) of allergy, asthma or eczema	Positive when 1 st degree of family members receive daily treatment for asthma or eczema. Or when a family member wears an epinephrine pencil because of a severe allergy.	

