11. STATISTICAL ANALYSIS

Continuous parametric data will be presented with mean \pm standard deviation (SD) or median with interquartile range (IQR) as appropriate. Categorical data will be presented as counts and percentages within each study group.

The cognitive test score of both cohorts will be compared with the Dutch average by using a linear regression model. The following potential confounders for cognitive development (IQ score) identified in earlier research will be used in the analysis;

- Sex
- Gestational age at birth
- Small for gestational age
- Neonatal morbidity
- Level of education of the parents

In second cohort; the FNAIT survivors with IVIg treatment atopic constitution and the course of infections will be assessed in a secondary analysis.

In the assessment of course of infections the following confounders will be used in the analysis by using a linear regression model;

- Day-care visit
- Smoking in a household
- Time of the year that the questionnaire was filled in

In the analysis of allergies and asthma the following confounders will be used in the analysis by using a linear regression model;

- Presence of a first degree family member with asthma eczema or allergy
- Smoking in a household

All data is analysed with IBM SPSS Statistics version 24 (IBM Software, NY, USA, 2016).

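### Day care is defined in the present tense with no exposure window, the infection look-back is unstated, and the infection model omits age, so the day-care covariate would largely stand in for young age

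*Combined protocol and SAP*

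**What the plan says.** Section 3.3 gives the reason for collecting the two exposures: for infections, "it is important to assess smoking at home and day-care visit as possible confounding factors". Section 9.1.3 adds only this on collection: "Also smoking and day-care visit will be questioned".

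Table 3, in the same section, holds the definitions. Day-care visit is "When child is in day care at least one day a week". Smoking is "Any person living in the household of the child smoking one or more cigarettes a day". Neither has an age range, a calendar period, or an ever/current distinction.

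The infection outcome in Table 3 is a need for referral to an immunologist, or for "diagnostics based on history taking according to the Dutch guidelines". Table 2 records it as yes or no over 2-18 years. No look-back period is given.

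Section 5.2 admits children "at moment of inclusion 2 to 16 years of age". Under section 9.3 the questionnaires are completed at home and brought to a single visit.

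Section 11 analyses infections in cohort 2 by linear regression with three covariates: day care, household smoking and "Time of the year that the questionnaire was filled in". The child's age is not among them. Table 1 (section 3.3) lists it as a potential confounder.

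**The concern.** An adjustment covariate should describe exposure in the period when the outcome arose. Here neither period is stated, so nothing shows that the two match. On its plain wording, the day-care item asks about attendance now. Take a 10-year-old who attended day care at 1 to 3 years and had recurrent infections then. That child would be coded no for day care, while the infections could still count if the history is cumulative.

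Leaving age out makes this worse. Few children beyond the pre-school years can be coded yes, so without age in the model the day-care coefficient mixes attendance with being a toddler.

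Infections are one of two immune outcomes that section 9.1.2 uses to look for long-term effects of maternal IVIg. What is at stake is whether the planned adjustment can be interpreted. Data are collected once, so early attendance that is not asked about cannot be recovered later without contacting families again.

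**Working it through.** The documents give no rate for day care, smoking or infections, so there is no figure of the plan to reproduce on this point. Cohort 2's planned size of 39 (section 5.4) is used below only for scale. It does reproduce: an exact one-sample t calculation with margin 7, SD 15 and one-sided 0.025 gives n = 39 with power 0.811.

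**Step 1: who can be coded yes if the item means current attendance.** From section 5.2, ages 2 to 16 make 15 age-years. The assumptions, which are not in the documents, are that ages are evenly spread and that day care ends at 4 or at 5.
- Ends at 4: ages 2-3, 2/15 = 13%; 39 × 2/15 = 5.2 children.
- Ends at 5: ages 2-4, 3/15 = 20%; 39 × 3/15 = 7.8 children.

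The other 80-87% of age-years would be no by construction. The 5 to 8 children are an upper limit, reached only if all of them attend.

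**Step 2: how well current status captures early attendance, with after-school care allowed to count.** Let f = 2/15 be the share aged 2-3, P the proportion who ever attended early day care, and r the proportion of early attenders aged 4 or over who still count as attending. Assume that all early attenders aged 2-3 still attend and that nobody else is coded yes. P = 0.4 to 0.8 and r = 0 to 0.2 are assumed ranges.
- Sensitivity: s = f + (1 − f)r
- Recorded yes: Ps
- Early attenders among those recorded no: P(1 − s)/(1 − Ps)
- Share of the variance of true early attendance explained: s(1 − P)/(1 − Ps)

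| P | r | s | recorded yes | of 39 | attended, among recorded no | variance explained |
|---|---|---|---|---|---|---|
| 0.4 | 0 | 0.133 | 0.053 | 2.1 | 0.366 | 0.085 |
| 0.4 | 0.2 | 0.307 | 0.123 | 4.8 | 0.316 | 0.210 |
| 0.8 | 0 | 0.133 | 0.107 | 4.2 | 0.776 | 0.030 |
| 0.8 | 0.2 | 0.307 | 0.245 | 9.6 | 0.735 | 0.081 |

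For example, with P = 0.8 and r = 0: 0.8 × 0.867/(1 − 0.107) = 0.776, and 0.133 × 0.2/0.893 = 0.030. Over these ranges, current status finds 13-31% of early attenders and explains 3-21% of the variance of early attendance.

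**Step 3: the two possible look-backs.**
- Lifetime or early childhood: step 2 applies, and adjustment for early day care is weak.
- Recent: current day care is the right exposure and a no at age 10 is a true value. By step 1 it is still largely determined by age, so without age in the model its coefficient cannot be separated from young age.

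Age belongs in the model on both readings. A record of early attendance is needed only on the first.

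**Step 4: smoking.** Household smoking does not switch to no at school age, so steps 1 and 2 do not carry over. What remains is that past smoking may be misclassified if only current smoking is recorded and the look-back is long.

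**The case against.** The strongest reply is that the plan leaves the windows open and does not fix them wrongly. Current status is inferred from verb tense. The questionnaire is not in the documents, and no section limits either item to the day of completion. This stands, so the defect is a missing specification and not a demonstrated measurement error. Table 3 is nevertheless the operative definition, and its plain reading is current attendance.

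Second, adjusting for season, "Time of the year that the questionnaire was filled in", makes sense mainly for recent infections, for which current exposure is correct. This also stands, but it does not remove the need for age.

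Third, the percentages rest on an assumed end of day care and an assumed age spread, and the protocol does not say whether after-school care counts. That is correct. The looser assumptions in step 2 reach the same qualitative result.

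A reader might go further and infer that the infection finding on IVIg is confounded by early day care or smoking. The documents do not support that. Section 11 places the analysis in cohort 2, where every mother received IVIg, and states no untreated or external comparator for infections. No treated-versus-untreated contrast is specified for day care to confound.

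A reader might also infer that day care is no for nearly all school-age children and cannot adjust at all. The documents give no attendance by age, so the supportable wording is that it adjusts poorly, under the stated assumptions.

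**Conclusion.** The point holds as a specification gap. The exposure windows for day care and smoking and the look-back for infections are unstated and not shown to match, and age, already named as a potential confounder, is missing from the infection model.

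If day care means current attendance, only about 13-20% of age-years can contribute a yes (even ages over 2-16, day care ending at 4 or 5). The covariate then acts largely as a marker of young age. If the infection history also reaches into early childhood, it captures an assumed 13-31% of early attenders. Smoking is a smaller matter of possible misclassification. The change is worth making because it is cheap and cannot easily be made after data collection, but it concerns a secondary outcome. The primary IQ analysis is unaffected.

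**What to change.** - Section 11: add age at assessment, already collected, to the infection covariates.
- Table 3, day-care visit: record (a) whether the child ever attended at least one day a week before school entry, with start and stop ages, and (b) current attendance at the same threshold. Say whether after-school care counts.
- Table 3, smoking: record past and current household smoking separately, keeping the existing threshold.
- Table 3 or section 9.1.2: state the look-back period of the infection questionnaire. In section 11, use the exposure variable that matches it.

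The guideline-based yes/no infection outcome should not be split into early and recent windows. That would ask some parents to recall infections from more than ten years back, in a study that already acknowledges recall bias (section 5.1), and the documents do not show that the criteria can be applied to a past window.

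The cost is a few recall questions on a form already sent home, some wording changes, and one more covariate in a cohort planned at 39. Adding age will not make the day-care effect precise: with perhaps 5 to 8 children young enough to attend, a current day-care coefficient will remain poorly estimated and should be reported as such.

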9.2 Randomisation, blinding and treatment allocation

Not applicable.

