Methods: Neurodevelopmental evaluation of the children will be performed, at a minimum age of 24 months. This includes an assessment of neurologic, motor and cognitive development using standardized psychometric tests appropriate for age and parent-report questionnaires on Health Related Quality of Life (HRQoL) and behavioral functioning. Academic trajectories of FNAIT children will be assessed by collecting test scores from the Dutch pupil monitoring system. We will assess allergies and the course of infections by questionnaires.

Main study parameters/endpoints: The primary outcome is cognitive development i.e., cognitive test score or Intelligence Quotient (IQ). Secondary outcome is neurodevelopmental impairment (NDI); a composite outcome including cerebral palsy Gross Motor Functioning

Classification System (GMFCS) \geq II, cognitive and/or motor test score of less than 70 (-2 SD), hearing loss requiring amplification or visual impairment (legally certifiable as blind or partially sighted). Other secondary outcome parameters are HRQoL and behavioral functioning and the academic performance. The course and incidence of infections and allergies will be assessed.

Nature and extent of the burden and risks associated with participation, benefit and group relatedness

The burden of neurodevelopmental assessment tests is minimal (e.g. 120 minutes at 2 to 6 years and 150 minutes at 7 to 17 years follow-up). Neurodevelopmental assessment is generally experienced as enjoyable for children. Parents will complete a HRQoL- and a behavioral questionnaire for their children. Academic performance will be evaluated by scores that were obtained at school. Participation does not result in any direct benefit.

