3. OBJECTIVES

3.1 Primary objective(s)

The primary objective is to determine the cognitive test score of children diagnosed with FNAIT without and with antenatal treatment. We will assess the neurodevelopmental outcome, with IQ score as outcome measure, of two groups:

Cohort 1: To evaluate the natural history of FNAIT, we will include in this first cohort all FNAIT survivors without antenatal treatment. Our hypothesis is that the cognitive test score in this cohort will be lower compared to the general population.

Cohort 2: To evaluate the safety and benefit of IVIg treatment, the IQ score in all FNAIT survivors treated with antenatal IVIg treatment will be determined. Our hypothesis is that the cognitive test score in this cohort is similar to the general population.

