5.4 Sample size calculation

Of note, performing sample size calculations in the context of this rare disease is difficult since literature is scarce and heterogeneous.

We performed two different sample size calculations for the two cohorts.

Cohort 1: Using the literature to date we estimated that the IQ score of FNAIT survivors without antenatal treatment is lower, that is 92 versus average (100) in the normal population. To show a difference in IQ score between FNAIT survivors without IVIg treatment compared to a fixed average of 100, we performed a sample size calculation for a one-sample t-test. We calculated that a minimum group size of 39 was needed to show a mean difference of 7 IQ points with a power of 0.8 and a significance of 0.05. We assume a standard deviation (SD) of 15 for the IQ score.

Cohort 2: In the FNAIT survivors with antenatal treatment we expect no difference in IQ score between cases and the national average. To show that there is no difference IQ score in anticipated IVIg treatment compared to the Dutch average we perform a non-inferiority calculation by a one-sample t-test. In this case we need a sample size of 39 children with a non-inferiority margin of 7 IQ points, with a power of 0.8 and a significance level of 0.025. We assume a standard deviation (SD) of 15 for the IQ score.

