9.3 Study procedures

[figure not shown]
After informed consent is obtained, assessment will be planned at the outpatient clinic of the LUMC. Questionnaires considering HRQoL, behaviour, allergies or infections will be sent home with the request to fill in the forms and bring them at the planned visit. We will

provide parents with a letter to request the most recent academic test scores from the teacher.

When parents visit the outpatient clinic with their children, the assessment will take place. No laboratory tests will be performed in this study, however data of the laboratory tests that were performed at timepoint of diagnosing FNAIT will be involved in this study. To gather important patient data from the pregnancy and neonatal period parents will be asked permission to obtain the medical letters from referral hospital of the child. Secondly mothers will be asked for informed consent to obtain the medical letter from the gynaecologist.

After assessment a report will be made from the observations during psychological testing.

Figure 2: Study procedures

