12.3 Objection by minors or incapacitated subjects

Neuropediatric examination and neurodevelopmental tests are performed by trained personnel who are in close contact with the child and parents to detect any resistance. All tests have age related items and can be performed in a playful way to avoid stress.

The investigators will follow the guidelines of the Dutch pediatric society concerning resistance or anxiety in minors during investigation procedures and the CCMO code of conduct concerning research with minors.

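### Section 9.2 treats blinding as not applicable, and nothing in the protocol text masks the examiners of the primary cognitive test, leaving a partly avoidable risk of cohort-specific assessor bias

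*Combined protocol and SAP*

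**What the plan says.** Section 9.2, headed "Randomisation, blinding and treatment allocation", consists only of a statement that it does not apply.

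The primary outcome in the Summary is a cognitive test score or IQ. Section 9.1.1 obtains it from the Bayley III, WPPSI III or WISC V according to age, alongside a formal neurologic examination. Section 12.3 says that these "neurodevelopmental tests are performed by trained personnel who are in close contact with the child and parents". Section 9.3 places the visit at the sponsor's outpatient clinic and says that "parents will be asked permission to obtain the medical letters from referral hospital of the child"; it does not say when the letters are read or by whom.

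Section 3.1 states what is expected in each cohort. For cohort 1: "Our hypothesis is that the cognitive test score in this cohort will be lower compared to the general population". For cohort 2: "Our hypothesis is that the cognitive test score in this cohort is similar to the general population". Section 5.4 tests cohort 2 as non-inferiority with a 7-point margin at 0.025. The comparator is a constant: cohort 1 is "compared to a fixed average of 100, we performed a sample size calculation for a one-sample t-test", and cohort 2 is set against the Dutch average.

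Section 5.1 gives survival and recall bias as examples of bias from the retrospective design. It does not mention assessor bias.

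**The concern.** Section 9.2 handles three different things with one entry. Treatment cannot be allocated or blinded retrospectively, but whoever gives and scores a test today can be kept unaware of cohort and history in any design.

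Three features make this worth attention.

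- The test is given in person, at a centre that is also the national referral centre for intrauterine therapy and that enrols families directly (Sections 4 and 12.2). An examiner could plausibly know the history.
- The protocol states in advance what each cohort should show.
- The comparator is a fixed norm. No control children are tested by the same examiners, so drift does not cancel.

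Cohort 2 matters most. Section 3.1 uses it to judge the safety and benefit of antenatal IVIg, and upward drift there would favour a finding of non-inferiority.

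**Working it through.** **Inputs.** From Section 5.4: SD 15, difference or margin of 7 points, power 0.80, significance 0.05 (cohort 1) and 0.025 (cohort 2), n = 39 per cohort. Assumed, because the documents give no value: a uniform examiner drift b of 1, 2 or 3 IQ points.

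**Step 1: reproduce the plan's figure.** For a one-sample t-test, SE = 15/√39 = 2.402. With 38 degrees of freedom the one-sided 0.025 critical value is t = 2.024. At a 7-point difference the noncentrality is 7/2.402 = 2.914, and the exact noncentral t gives power 0.811. The smallest n with power of at least 0.80 is 39, as stated. For cohort 1 this requires 0.05 to be two-sided; one-sided 0.05 would give 30.

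**Step 2: add a drift.** For cohort 2, take the true mean at the margin, 100 − 7 = 93, where non-inferiority should be declared 2.5% of the time. If scores are raised by b, the test statistic is noncentral t with 38 degrees of freedom and λ = b/2.402, so

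P(false non-inferiority) = 1 − F(2.024; 38, λ).

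For cohort 1, take a true mean of 100 with scores lowered by b. The chance of a false finding of a lower mean is the same expression. The two-sided total adds the small opposite tail.

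| Drift b | λ = b/2.402 | Cohort 2: false non-inferiority (true mean 93) | Cohort 1: false significance, two-sided (true mean 100) |
|---|---|---|---|
| 0 | 0 | 2.5% | 5.0% |
| 1 | 0.416 | 6.0% | 6.9% |
| 2 | 0.833 | 12.5% | 12.8% |
| 3 | 1.249 | 22.9% | 23.0% |

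**Step 3: drift in the other direction.** If examiners instead scored cohort 2 low because they know the children had FNAIT, and the true mean is 100, then λ = (7 − b)/2.402. Power falls from 81.1% to 68.2%, 52.7% and 36.8% for b = 1, 2 and 3.

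**Step 4: sample size does not help.** Since λ = b√n/15, a fixed drift weighs more as n grows. Masking leaves the required n unchanged.

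**The case against.** **The evidence is silence.** Section 9.2 sits among intervention-trial headings (Sections 6 to 8) that are also marked not applicable, so the entry may mean treatment blinding only. Figure 2, the procedures flow, could not be read. This stands: a reader might infer that examiners do know cohort and history, but the documents do not say so. They only fail to prevent it.

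**Only cohort 1's hypothesis is directional.** A reader might infer a directional hypothesis in both cohorts, with each pushed towards its own result. Section 3.1 does not support that: cohort 2 is expected to be similar to the general population, and it is the non-inferiority test that makes one direction favourable. An examiner expecting normal scores need not inflate them, and one who knows of FNAIT might score low (Step 3). The direction of any drift is not settled.

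**Existing safeguards.** The Summary specifies standardised tests and Section 12.3 trained personnel, and both limit drift. The school scores in Section 9.1.2 do not come from study examiners and give a partial outside check for school-age children. They are secondary and do not protect the primary outcome.

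**Masking cannot be complete.** Every child has FNAIT, and examiners know it. Hiding cohort, IVIg and ICH removes cohort-specific expectation, but not the knowledge that an affected group is being set against a norm. This stands.

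**Staffing.** The protocol does not say whether those who telephone families (Section 12.2) or handle the letters also do the testing. It cannot be assumed that masking works everywhere with the present staff.

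**Conclusion.** The point holds as a gap in protection, not as a demonstrated bias. The text leaves examiners of the primary outcome unmasked by default, with an expected result stated for each cohort and a fixed comparator. The resulting risk of cohort-specific assessor bias is partly avoidable.

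The table shows how sensitive the tests are to bias; it does not estimate the bias. It rests on a uniform drift of 1 to 3 points that has no source in the documents, on true means placed exactly at 93 and 100, and on the one-sample t-test of Section 5.4 rather than the regression of Section 11. Under those assumptions false non-inferiority rises from 2.5% to between 6.0% and 22.9%, and two-sided false significance in cohort 1 from 5.0% to between 6.9% and 23.0%. It would go too far to read these as the study's actual error rates, or to conclude that masking would restore the nominal ones. This is a worthwhile, inexpensive improvement to the plan; it does not invalidate the design.

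**What to change.** Replace the blinding entry in Section 9.2 with a short statement that:

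- among existing staff, and where feasible, the person giving and scoring the cognitive test and neurologic examination is not told cohort, maternal IVIg exposure, ICH or neonatal course;
- the visit letter asks parents not to mention these before testing ends;
- the medical letters are opened to the examiner only after scores are locked in the eCRF, and the report for parents is written after that;
- any unmasking is recorded, with its source, and reported with the results.

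In Section 5.1, name residual assessor bias against the norm beside survival and recall bias.

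The cost is mainly the order of work around the visit, a sentence in the visit letter and one eCRF field. Sample size is unchanged. The downside is that masking will be partial: FNAIT status is known to examiners, visible impairment or parents may reveal the history, and staff who contacted the family may already know it. Where no unaware member of staff is available, recording what the examiner knew is still better than the present entry.
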